**9. Other Cardiovascular Death:**

Death resulting from a specifically documented cardiovascular cause other than those listed above.

Heart failure hospitalization also includes the development of new symptomatic heart failure during an ongoing hospitalization including the index AMI hospitalization.

Outpatient heart failure is defined as:

- An urgent/unscheduled visit to an ED, acute/urgent care facility or outpatient clinic or a non-urgent office/practice or study visit for a primary diagnosis of HF that does not require an overnight hospital stay.

- Patients must exhibit at least one documented new HF symptom with objective evidence of clinical HF consisting of at least 2 physical examination findings or one physical examination findings and at least one laboratory criterion.

- The event requires initiation or intensification of treatment specifically for HF.

Such treatment can include administration of intravenous agent (e.g., diuretic, vasodilator, vasopressor, or inotrope) or mechanical or circulatory intervention for HF, OR initiation of oral loop diuretic treatment, or intensification of oral maintenance loop diuretics for the diagnosis of HF, over a sustained period (i.e., initiation or doubling of total daily dose through a period of  $\geq 4$  weeks), which is confirmed at a subsequent outpatient visit.

#### **7.4.4 Biomarkers**

Biomarker measurements will be obtained from serum and plasma in a subset of patients at selected sites before surgery and at Visits 1, 2, 3 and 4 to determine effects of treatments on biomarkers of STEMI after PCI.

Biomarkers studied include:

NT-proBNP

Details on sample collection, handling and shipment of biomarker samples will be provided to investigators in the laboratory manual.

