## **4 Study design**

This study is a single-center, prospective, randomized, double-blind, parallel-group, two-arm, short-term trial to compare sacubitril/valsartan 200 mg bid to enalapril 10 mg bid in concentration of NT-proBNP reduction and main cardiac ultrasound parameters improvement in patients with acute anterior STEMI after PCI.

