### **4.1 Justification of key elements of the study design**

#### **4.1.1 Selection of the primary endpoint**

We chose NT-proBNP as the primary endpoint in this study because natriuretic peptide concentrations are associated with adverse outcomes in patients with AMI. Although both ANP and BNP undergo degradation by neprilysin, the biologically inert NTproBNP, cleaved from proBNP along with BNP, is not a substrate for neprilysin degradation, and changes in this marker still reflect reduction in left ventricular wall stress even in the setting of neprilysin inhibition.

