#### **4.2.4 Follow-up period**

##### **Visit 4 (Follow-up Visit)**

Follow-up visits are scheduled for Weeks 4, 12 and 24. Blood and urine samples are sent to a central laboratory for hematology, chemistry, and serum and urinary biomarkers. Professionals use Philips IE33 ultrasound system (Philips Medical System, Bothell, Washington, USA) for echocardiographic measurements. In addition to the protocol-required visits, patients may be seen at any time throughout the study at the discretion of the investigator to investigate or follow any new lab abnormalities or adverse events.

Monitoring of safety and tolerability will include: (1) hyperkalemia; (2) symptomatic hypotension; (3) increase in serum creatinine; (d) angioedema; and (e) adverse events and serious adverse events. If, in the opinion of the investigator, the patient cannot tolerate the target dose of study drug, the investigator should consider whether non-life saving medication (e.g., CCBs, nitrates,  $\alpha$ -blockers) can be reduced to rectify the situation before considering reducing the dose of the study drug to the lower dose level. The dose of background disease modifying drugs, such as  $\beta$ -blockers and mineralocorticoid receptor antagonists, should not be reduced to facilitate maintenance of study drug. If the situation is not rectified despite adjusting/discontinuing nonlife-saving medications or if adjusting non-life-saving concomitant medications is not possible, patients who no longer tolerate the target dose at any time during the course of the trial can be down-titrated to the lower dose level at the investigator's discretion (please refer to Figure 1 for dose levels available for titration). However, every attempt should be made to re-challenge the patients so that they are kept on the maximal tolerated dose of study drug for as long a duration as possible throughout the outpatient

dose titration and follow-up period of the trial. Please refer to Section 6.4.3 for a guidance on study drug dose adjustment.

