## **10 Data analysis**

### **10.1 Populations for analysis**

The full analysis set (FAS) will consist of all randomized patients. Following the intent-to-treat principle, patients will be analyzed according to the treatment to which they were assigned at randomization. Efficacy variables will be analyzed based on the FAS as the primary population.

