#### **10.3.1 Primary efficacy variable**

The primary efficacy outcomes are the changes in NT-proBNP concentrations from baseline through weeks 4, 12 and 24 and in echocardiographic parameters (LVEF, LVEDV, LVESV) from baseline through weeks 12 and 24.

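### Section 7.4.4 limits NT-proBNP measurement to an undefined subset, contradicting its status as a primary outcome analyzed in all randomized patients of a single-center trial

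*Protocol*

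**What the plan says.** Section 7.4.4 is where the protocol sets out how the biomarker is obtained: "Biomarker measurements will be obtained from serum and plasma in a subset of patients at selected sites", before surgery and at Visits 1 to 4. Under "Biomarkers studied include" it names one marker, NT-proBNP. It gives neither the size of the subset nor a rule for choosing it.

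The rest of the protocol treats the same marker as primary:

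- Section 4.1.1: "We chose NT-proBNP as the primary endpoint in this study".
- Section 7.4.1 lists it first among four primary outcomes, with LVEF, LVEDV and LVESV.
- Section 10.3.1: "The primary efficacy outcomes are the changes in NT-proBNP concentrations from baseline through weeks 4, 12 and 24"; the echocardiographic changes follow at weeks 12 and 24.
- The synopsis and sections 1, 2, 3.1 and 10.3 give it the same role.

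On the analysis population, section 10.1 states "The full analysis set (FAS) will consist of all randomized patients" and "Efficacy variables will be analyzed based on the FAS as the primary population". On the number of centers, section 4 states "This study is a single-center, prospective, randomized, double-blind, parallel-group, two-arm, short-term trial"; the synopsis and section 1 agree.

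**The concern.** A primary outcome has to be collected in everyone in whom it will be analyzed. If section 7.4.4 is followed, an unstated share of randomized patients will have no NT-proBNP value, and the analysis promised in section 10.1 cannot be carried out for that outcome. An analysis plan cannot repair this, because it cannot recover samples that were never taken.

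Two things are at stake. One is precision, since fewer patients contribute. The other is comparability of the arms: without a selection rule, the reader cannot exclude that being sampled depends on prognosis or on events after randomization, and cannot tell planned non-sampling from missing data.

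**Working it through.** **Text comparison**

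| Question | Section 7.4.4 | Elsewhere in the protocol |
|---|---|---|
| Who has NT-proBNP measured? | A subset, size and rule not given | All randomized patients are needed (10.1 with 10.3.1) |
| Where? | At selected sites | One center (synopsis, 1, 4) |
| Status of the marker | Only biomarker listed | Primary outcome (4.1.1, 7.4.1, 10.3.1) |

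I then looked for text that would override 7.4.4.

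- Section 4.2.4 says "Blood and urine samples are sent to a central laboratory for hematology, chemistry, and serum and urinary biomarkers", with no subset limit, but it does not name NT-proBNP. The synopsis has a near-identical sentence.
- Section 1 mentions blood tests at 4, 12 and 24 weeks, again without naming the marker.
- Table 7-2, the routine laboratory list, includes high-sensitivity troponin I but not NT-proBNP, so the routine panel does not guarantee it.
- I place no weight on Table 7-1, because its extraction may be incomplete.
- Section 7.4.5 sets no subset for echocardiography, so the restriction touches one of the four primary outcomes.

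**The plan's own figure (section 10.6)**

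Inputs: LVEF difference 3 points, SD 6 points, 1:1 allocation, α = 0.05, power 80%. Sidedness is not stated.

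- Standardized difference: 3/6 = 0.5.
- Normal approximation, two-sided: n = 2(1.960 + 0.842)²/0.5² = 62.8, so 63 per arm. The t-test version gives 63.8, so 64, as stated. A one-sided test would give 50 and does not match.
- Loss to follow-up: 128/0.90 = 142.2, against the stated 142.

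The sample size reproduces. It rests on LVEF, and the point made here does not change it.

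**Illustration of the precision loss**

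The protocol gives no effect size or SD for NT-proBNP and no subset size, so all of the following is assumed: an effect of 0.5 SD on log NT-proBNP, an unadjusted two-sample t-test, two-sided α = 0.05, and 64 evaluable patients per arm if everyone is measured. With a fraction f measured, each arm has 64f patients and the standard error grows by 1/√f.

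| Fraction measured | Per arm | Standard error multiplier | Power at 0.5 SD | Effect detectable with 80% power |
|---|---|---|---|---|
| 100% | 64 | 1.00 | 80% | 0.50 SD |
| 75% | 48 | 1.15 | 68% | 0.58 SD |
| 50% | 32 | 1.41 | 50% | 0.71 SD |
| 25% | 16 | 2.00 | 28% | 1.02 SD |

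**The case against.** The strongest reply is that the phrase is a remnant. A single-center trial has no sites to select among, follow-up blood is described elsewhere without a subset limit, and section 7 has all patients attend the scheduled visits. Full sampling may well be what is meant. That is plausible, and it is why this is better called an internal contradiction than a deliberate design. It does not remove the problem: no other text names NT-proBNP as sampled in everyone, and section 12 permits no authorized deviations and routes changes through an amendment. Staff would have to either follow 7.4.4 and lose primary data or depart from its text.

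A second reply is that the power figures do not describe this endpoint. That also stands. The 0.5 is the LVEF assumption, the protocol does not power NT-proBNP, and section 10.3.2 specifies a baseline-adjusted analysis of covariance on the log scale, not a t-test. The figures show how quickly precision falls as sampling shrinks, and no more.

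Three stronger readings are tempting and are not supported:

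- That the whole primary analysis fails. Three of the four primary outcomes carry no such restriction.
- That many patients would go unmeasured by design. No subset size is given, so the number is unknown.
- That the subset is non-random, or that staff choose it. Section 7.4.4 is silent on both; all that can be said is that no selection rule is given.

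**Conclusion.** The contradiction is certain and lies within the current text: section 7.4.4 cannot be reconciled with sections 7.4.1, 10.1 and 10.3.1 or with the single-center design. Its consequence is confined to the NT-proBNP comparison. The size of that consequence is unknown, because neither the subset fraction nor an NT-proBNP effect is stated; the tabulated loss is conditional on the assumptions given with it. Selection bias is a possibility left open by the missing rule, not something the protocol shows will occur. The point should be fixed before sampling starts, since uncollected samples of a primary outcome cannot be recovered.

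**What to change.** In section 7.4.4, replace the restriction to a subset at selected sites with a requirement to measure NT-proBNP in all randomized patients. State that the samples include the baseline as section 10.2 defines it (last value before the first randomized dose) and weeks 4, 12 and 24, to match section 10.3.1. Keep the other time points already listed there. Add NT-proBNP to Table 7-2.

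If a subset is truly intended, remove NT-proBNP as a primary outcome everywhere it is so named (the synopsis and sections 1, 2, 3.1, 4, 4.1.1, 7.4.1 and 10.3) and label it exploratory. Changing only some of these places would create new contradictions.

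The first option costs a short amendment and one added assay, since blood already goes to the central laboratory at these visits (sections 4.2.4 and 7.5.4). The sample size stays at 64 per arm and 142 in total.

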#### **7.4.5 Cardiac ultrasonic parameters**

Professionals use Philips IE33 ultrasound system (Philips Medical System, Bothell, Washington, USA) for echocardiographic measurements after PCI and 12 and 24 weeks after discharge. Use the biplane Simpson method to measure LVEDV, LVESV and LVEF in the apical four-chamber heart and two-chamber heart views according to

the recommendations issued by the American Society of Echocardiography and the European Cardiovascular Imaging Association.

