## **1 Background**

Angiotensin receptor-neprilysin inhibitor (ARNI, Sacubitril/Valsartan) is superior to angiotensin-converting enzyme inhibitors (ACEI) on cardiac remodeling in patients with heart failure (HF). However, there is little data describing the effects of sacubitril/valsartan in patients with acute anterior ST-segment elevation myocardial infarction (STEMI). The objective is to assess the safety and efficacy of sacubitril/valsartan compared with Enalapril in patients with acute anterior STEMI after PCI.

This study is a single center, prospective, randomized, double-blind trial, planning to recruit patients with acute anterior STEMI at the Second Affiliated Hospital of Nanchang University. Patients are randomly assigned 1:1 to in-hospital initiation of sacubitril/valsartan and enalapril. The starting dose during the in-hospital initiation phase and all subsequent dose changes during the titration period is selected using a dose titration algorithm (Figure 1). Patients are followed up at 4, 12, and 24 weeks after discharge from the hospital, blood test and echocardiograph are performed. The primary efficacy outcomes are the changes in NT-proBNP concentrations and in echocardiographic parameters (LVEF, LVEDV, LVESV) from baseline through weeks 4, 12 and 24. Secondary outcomes include the incidence of a composite of death, reinfarction, hospitalization for heart failure or outpatient heart failure, arrhythmia, stroke. Safety endpoints are the incidence of angioedema, hypotension, renal insufficiency, and hyperkalemia.

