### **4.2.2 Randomization**

#### **Visit 2 (Randomization Visit)**

Patients who have met all the inclusion criteria and none of the exclusion criteria at the end of the screening period will be randomized to either enalapril or sacubitril/valsartan in a 1:1 ratio. Patients randomized to enalapril continue to receive enalapril, while

patients randomized to sacubitril/valsartan discontinue enalapril to ensure a minimum 36-hour washout period prior to initiation of ARNi therapy. The first dose of sacubitril/valsartan is followed by 6 hours of monitoring for hypotension. After the condition is stable, patients can be discharged from the hospital at any point in time at the discretion of the clinician-investigator. The starting dose during the in-hospital initiation phase is selected using a dose titration algorithm based on systolic blood pressure (SBP) (Figure 1).

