### **10.2 Patient demographics/other baseline characteristics**

Baseline value is defined as the last non-missing assessment prior to the first dose of randomized study medication unless specified otherwise. Summary statistics will be provided by treatment group for demographics and baseline characteristics, including age, sex, weight, height, body mass index (BMI), Previous history of hypertension, prior history of Diabetes mellitus, Previous smoking history, Killip class, blood tests, Number of diseased vessels, vital signs, etc. BMI will be calculated as  $\text{weight (kg)} / \text{height}^2 \text{ (m}^2\text{)}$  from the collected height and weight at Visit 1 (Screening Visit). Continuous variables will be summarized using n, mean, standard deviation, geometric mean and 95% confidence interval. Categorical variables will be summarized using frequency and percentage.

The difference between treatment groups will be compared using the Fisher's exact test for categorical variables or using t-test or Mann-Whitney U test for continuous variables. The p-values will be provided for descriptive purposes and will not be considered to define any formal basis for determining factors to be included in statistical models.

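### Follow-up weeks are counted from discharge in some sections and from no stated origin in others, the baseline cut-off is ambiguous between arms, and sections disagree on whether echocardiography at week 4 is a primary assessment

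*Protocol*

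**What the plan says.** **Time origin.** Section 1: "Patients are followed up at 4, 12, and 24 weeks after discharge from the hospital, blood test and echocardiograph are performed". Section 7.4.5 schedules echocardiography "for echocardiographic measurements after PCI and 12 and 24 weeks after discharge". The synopsis (Visit 4) and section 4.2.4 say only "Follow-up visits are scheduled for Weeks 4, 12 and 24", with no origin. Table 7-1 labels the randomization visit as week -1 to -0 and numbers the later visits 2w, 4w and so on. Its week numbers therefore start after the randomization period, but the event that defines week 0 is not named.

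**Discharge.** Under the synopsis and section 4.2.2, once stable, "patients can be discharged from the hospital at any point in time at the discretion of the clinician-investigator". The same paragraph has enalapril patients simply continue their drug. Sacubitril/valsartan patients stop enalapril for at least 36 h, and their first dose is followed by 6 h of monitoring.

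**Baseline.** Section 10.2: "Baseline value is defined as the last non-missing assessment prior to the first dose of randomized study medication unless specified otherwise".

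**Echo time points.** Section 1 defines the primary outcome as change "in echocardiographic parameters (LVEF, LVEDV, LVESV) from baseline through weeks 4, 12 and 24". Section 10.3.1 defines it as change "in echocardiographic parameters (LVEF, LVEDV, LVESV) from baseline through weeks 12 and 24".

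**The concern.** A follow-up clock should start at an event that treatment assignment cannot move, and randomization is that event. Discharge comes after randomization, is discretionary, and in one arm has to follow steps that the other arm does not have. If discharge comes later in the sacubitril/valsartan arm, its week-4 sample is taken later after the infarct. A marker that is still falling would then read lower in that arm without any drug effect. Even with no systematic difference between arms, patient-to-patient variation in length of stay adds timing noise to the primary variables.

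The baseline rule has a related weakness. It sets a cut-off by first dose, not by randomization, and the first dose is not a comparable event in the two arms. Baseline is the covariate in the primary analysis of covariance (section 10.3.2), so the value that counts has to be fixed.

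The echo conflict is simpler. Sites cannot tell whether a week-4 scan is required, and the list of primary comparisons depends on which section is read. LVEF is also the variable that drives the sample size (section 10.6). A scan that was not done cannot be recovered at the analysis stage.

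**Working it through.** **1. The plan's own figures.**
- Washout: section 6.4.2 puts doses at about 08:00 and 19:00. In the section 7 example, Visit 2 is Wednesday, the last enalapril dose is Tuesday evening and the first sacubitril/valsartan dose is Thursday morning. Tuesday 19:00 to Thursday 08:00 is 5 + 24 + 8 = 37 h, which meets the 36 h minimum.
- Sample size (difference 3, SD 6, two-sided 0.05, power 80%): the normal formula gives 63 per group and the t-test 63.8, so 64; 128/0.9 = 142.2. This reproduces and is not in dispute.

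**2. Lag of the first sacubitril/valsartan dose behind the first enalapril dose after randomization.**

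| Last enalapril dose | First sacubitril/valsartan dose | Enalapril dose compared | Lag |
|---|---|---|---|
| Tue 19:00 (section 7 example) | Thu 08:00 | Wed 08:00 | 24 h |
| Tue 19:00 (section 7 example) | Thu 08:00 | Wed 19:00 | 13 h |
| Wed 19:00 (washout starts after a Visit 2 dose) | Fri 08:00 | Thu 08:00 | 24 h |
| Wed 08:00 (washout starts after a Visit 2 dose) | Fri 08:00 | Wed 19:00 | 37 h |

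The range is 13 to 37 h: 13/24 = 0.54 to 37/24 = 1.54 days.

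**3. Earliest end of monitoring.** Adding 6 h to the example gives Thursday 14:00. That is 24 + 6 = 30 h (1.25 days) after a Wednesday 08:00 Visit 2 (clock time assumed). This is the earliest exit in one arm, not a difference in discharge between arms; the documents give no such difference. As a share of elapsed time, 1.25 days is 1.25/28 = 4.5% at week 4, 1.25/84 = 1.5% at week 12 and 1.25/168 = 0.7% at week 24.

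**4. Illustration for week-4 NT-proBNP.** All inputs except the 64 per arm and the 30 h are assumptions. Suppose discharge really differed by 30 h and NT-proBNP were still falling with a half-life of 14 to 60 days.
- Shift on the log scale = ln 2 × 1.25 / half-life = 0.062 (14 days) or 0.014 (60 days), a reading 6.0% or 1.4% lower.
- With a log-scale SD of 0.8 to 1.0, the standard error is SD × √(2/64) = 0.14 to 0.18.
- The shift is then 0.062/0.141 = 0.44 standard errors at one extreme and 0.014/0.177 = 0.08 at the other.
- If discharge days do not differ between arms, the shift is zero.

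**5. Baseline.** Section 7.4.4 samples NT-proBNP before surgery and at Visits 1 and 2. Sections 4.2.1 and 4.2.2 allow enalapril before randomization. In the enalapril arm, the first dose of randomized medication could therefore mean the first dose after Visit 2 or a dose already taken, and the two readings can select different samples. In the other arm the cut-off falls after randomization, so a sample drawn during washout would qualify as baseline. No assessment is scheduled in that interval.

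**6. Echo schedule.**

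| Section | Echo follow-up |
|---|---|
| 1 (procedures and primary outcome) | weeks 4, 12, 24 |
| Synopsis Visit 4 and 4.2.4 | described with the week 4, 12, 24 visits |
| 7.4.5 | weeks 12, 24 |
| 10.3.1 (primary variable) | weeks 12, 24 |

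With three echo parameters, that is 3 × 3 = 9 primary echo comparisons under section 1 and 3 × 2 = 6 under section 10.3.1.

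**The case against.** The strongest reply is that no timing bias has been shown. These are patients after emergency PCI, and the washout may fall within a stay that both arms would have anyway. Discharge depends on stability and discretion in both arms, and in a trial described as double-blind it should not depend on assignment. No assessment is scheduled between Visit 2 and first dose, last value before first dose is a common baseline rule, and section 10.2 leaves room for exceptions. Section 6.4.3 also asks for visits close to the Table 7-1 time points. On echo, the two operative sections (7.4.5 and 10.3.1) agree with each other.

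Much of this stands, and it limits the size. A reader might add 36 h and 6 h and conclude that discharge and baseline both come about two days later in the sacubitril/valsartan arm, with a clearly inflated false-positive rate. The documents do not support that. The 42 h runs from the last enalapril dose, which in the section 7 example precedes Visit 2. It is not a between-arm discharge difference. A baseline taken later in that arm, while NT-proBNP is falling, would work in the opposite direction to a later follow-up.

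What the reply does not remove is the wording. Two sections use a post-randomization origin, others give none, and Table 7-1 does not name its week 0. The intended blinding does not help here, because section 4.2.2 attaches the extra steps to one arm only. The week-4 echo appears in section 1 as a primary outcome, not only as a procedure, and the synopsis and section 4.2.4 lean the same way.

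**Conclusion.** The point holds in a limited form. The plan lets the timing of primary assessments relative to infarct and randomization differ by arm, and its baseline cut-off is ambiguous. The discharge lag cannot be computed from the documents and may be zero. The first-dose lag is about 0.5 to 1.5 days, given the stated dose times and depending on when the last enalapril dose falls. Any effect is probably small and mainly confined to NT-proBNP at week 4; a day or so matters little at weeks 12 and 24. The illustrated shift rests on an assumed half-life, SD and discharge difference, so it shows scale and does not estimate bias.

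The echo conflict needs no assumption. The sections differ by three primary comparisons and on whether a week-4 scan takes place. The sample size is unaffected. The sponsor should correct this, chiefly because the correction is cheap and settles what the primary outcomes are.

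**What to change.** 1. In the synopsis (Visit 4), sections 1, 4.2.4 and 7.4.5, and Table 7-1, state that weeks 4, 12 and 24 are counted from randomization (Visit 2) in both arms.
2. In section 10.2, define baseline as the last non-missing value before randomization in both arms, for NT-proBNP and for echocardiography.
3. Use one echo schedule in the synopsis and in sections 1, 4.2.4, 7.4.5 and 10.3.1: baseline, week 12 and week 24, as section 10.3.1 has it. Remove week-4 echo from section 1, and make clear in the synopsis and section 4.2.4 that the week-4 visit does not include a scan.

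The cost is a wording amendment. Visit dates move by the interval between randomization and discharge, no assessment is added, and the sample size stays the same. The change concerns only how time is counted and which value is baseline; it leaves washout, monitoring, titration and discharge as they are.
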